#### **iii. Recruitment/Enrollment:**

Active recruitment will be carried out by study front-line staff, who will be members or allies of the target population. Participants will be recruited actively at the TLC drop-in center, "TransSafe" (or virtual TLC drop-in center or via virtual TLC services, during COVID-19 restrictions) by study staff and staff will visit local gathering places of TW, such as night clubs,

pageants/balls and public places, such as local parks, to identify and recruit potential participants. Participants will also be asked to refer friends or others who that may be eligible. Passive approaches include posting of study flyers (see Recruitment materials, Appendix a).

Interested participants will be screened for eligibility either in person, over the telephone, or via teleconference prior to enrollment (see Study Screener, Appendix b). The screening script includes a brief description of the research study and procedures and related risk and indicates that participation is voluntary and confidential. No identifying information or contact information will be collected from participants who are ineligible for the study. The screening form briefly describes the study and procedures, indicates participation is voluntary and confidential, and briefly describes risks and benefits of participation. Screening failures and reasons for ineligibility will be carefully tracked.

Immediately following screening (or as soon as possible thereafter if screening occurs by telephone; re-screened if more than 30 days elapses after initial screening), participants who are eligible and interested in participation will be consented for participation and enrolled (see Locator and Consent forms, Appendices c-d).

**c. Data Collection**

Study visits will be completed at Chicago House, or Lurie Children's facilities/locations except in cases in which travel to study sites is not possible due to scheduling difficulties, moving from the local area, or due to COVID-19 restrictions, in which case a remote version of computerized questionnaires may be completed. During the COVID-19 pandemic, visits may be conducted in-person, using precautions, or remotely via telephone or web-based telemedicine conference. Chicago House has adopted HIPAA compliant Doxy.me telehealth software for use during the pandemic, which will also be used to conduct remote research visits. TLC intervention participants will complete computerized assessments through interviewer and self-administration modes at three separate assessment visits (baseline, 4, and 8 months; see Data Collection Instruments, Appendix e.). Study assessments will include report of demographic characteristics and psychosocial factors (substance use, mental health symptoms), sexual risk behavior- the primary outcome, PrEP care engagement- secondary outcome, intervention mediators (gender affirmation, collective self-esteem, social support) and intervention satisfaction (4 and 8-months only). All variables will be measured at all time points unless otherwise specified (see Table 2). Medical records abstraction will be completed by the study data manager with training for the abstraction process conducted by [name].

**Table 2. Study Trial Outcomes by Type, Construct, Measure & Time Point (see Citations in III.c.i)**

Outcome Type	Construct	Measure	Baseline	4 month	8 month
Primary Outcome:	Sexual Risk	ARBA	•	•	•
Secondary Outcomes:	PrEP care engagement	Self-report care linkage, initiation, retention Medical records abstraction	•	•	• •
Mediators:	Gender affirmation Collective self-esteem Social support	GEN AFFIRM, CSES SS items	• • •	• • •	• • •
Demographic & Psychosocial Factors:	Demographics Substance use Depressive symptoms Anxiety symptoms Victimization	Demographic items ASSIST CES-D GAD-7 Victimization scale	• • • • •	• • • • •	• • • • •

Satisfaction/Acceptability:	Acceptability Satisfaction Intervention dosage	Acceptability items CSQ Intervention exposure		• • •	• • •
Biological Markers	PrEP protection HIV Infection STI Infection	PrEP Hair analysis/DBS* 4 th generation HIV algor* Chlam/GC AMP Probe* Syphilis Health Check/RPR*	• • • •	• • • •	• • • •

Participants who withdraw from the study voluntarily or who are administratively withdrawn will be carefully tracked via a tracking log with reasons recorded for withdrawal.

\*During the COVID-19 pandemic, PrEP hair analysis/DBS, Chlam/GC, and Syphilis Health Check will not be collected at any time point. HIV testing will be completed at the baseline visit only.

### **i. Variables**

*Primary outcome:* The primary outcome, condomless anal sex acts not protected by PrEP adherence (defined as anal sex acts without a condom in the prior month without use of PrEP at protective levels) will be analyzed as a composite variable of condomless anal sex acts that confer risk in the prior month, adjusting condomless acts to “0” for those participants with protective levels of PrEP adherence verified by biomarker (i.e., hair analysis, see below). We will use the AIDS-Risk Behavior Assessment (ARBA; revised for transgender women) for measurement of sexual risk. The ARBA is a computerized self-interview designed to assess self-reported sexual behaviors. Self-reported PrEP adherence will be measured using time-line follow-back (TLFB) for the 1-month recall period. Objective verification via hair samples will only be completed for those individuals who report levels of adherence consistent with protection over the entire recall period (i.e., 4 doses/week for PrEP). We will collect hair samples (100 strands) for analysis of uptake/adherence to PrEP (tenofovir disoproxil fumarate). Hair analysis will be completed at the University of California (UCSF) Hair Analysis Lab. Among participants from whom a hair sample is not feasible, either due to short hair or hair extensions, for example, a blood sample will be collected via a dry blood spot (DBS), for analysis of PrEP level. The DBS will be collected by venipuncture (4mL of blood or approximately one teaspoon). DBS processing and analysis will be performed by University of Colorado. During the COVID-19 pandemic, no hair or DBS samples will be collected at any time point.

*Secondary outcomes:* PrEP continuum outcomes, including PrEP linkage to care, PrEP initiation and retention in PrEP care will be measured using self-report with confirmation via medical records abstraction with a release of information (NB: release of information to be updated at each visit; abstraction timed to occur immediately after the 8-month visit, see Release of Information, Appendix f.; Case Report Forms, Appendix g.): 1) Linkage to PrEP care is defined as attending at least one PrEP-related care visit to assess medical eligibility for PrEP initiation; 2) PrEP initiation questions will measure the date of initiation of medication, current use and most recent date the medication was taken; 3) Retained in PrEP care will be measured over the 8-month follow-up interval as at least 1 primary care visit over the 8-month follow-up period.

*Psychosocial Mediators* Gender Affirmation is a 10-item measure that assess adjustment and experiences that are specific to gender identity and gender affirmation. The Collective Self-Esteem Scale (CSES)/Empowerment is a 16-item measure with 4 subscales of social group and empowerment: membership, private, public, and identity. The scale was modified to capture “social group” as being “other transgender people” for TW in our ongoing RCT. Social support will be measured with peer social support measures used in prior studies of transgender women.

*Demographic and Psychosocial Factors:* We will measure age, race/ethnicity, and other demographics (i.e., income, education, school status) using standard questions used in prior research with TW. Within this assessment of demographics, we will measure housing, employment, legal and medical care status more specifically to track changes over time. We will also measure psychosocial factors, given the prevalence of these conditions in TW, and assess their distribution in the sample at baseline and over time. Among the psychosocial factors measured include substance use, depression and anxiety symptoms, and experiences of victimization. To measure substance use we will use the World Health Organization Alcohol, Smoking, and Substance Involving Screening Test (ASSIST), which includes assessment of 10 substances and related problems. To measure depression and anxiety symptoms we will use widely used screening tools: the Center for Epidemiologic Studies Depression Scale (CESD-10) and the Global Assessment Generalized Anxiety Disorder Scale (GAD-7), respectively. To measure victimization we will use the 10-item Victimization Scale, which includes questions related to both verbal and physical abuse.

*Intervention Satisfaction and Acceptability:* To measure acceptability, we will ask participants to report the degree to which they find the intervention appropriate and useful using Likert-type scales. To measure satisfaction, we will use the Client Satisfaction Questionnaire to assess participant satisfaction, including the procedures, quality and quantity of service, outcome, and general satisfaction. The CSQ-8 has high internal consistency across a large number of studies ( $\alpha > 0.80$ ) and has been used in prior studies of TW. Intervention dosage. Delivery of the intervention will be measured via tracking of intervention participation in attendance logs maintained within each component of the TLC program (see Case Report Forms, Appendix g).

*Biological specimens/Biomarkers.* STI/HIV screening will include a rapid HIV test via oral fluid or finger stick, self-collected urine and anal swab specimens for chlamydia and gonorrhea testing, and finger stick (rapid test) or blood draw for syphilis testing. Participants with a reactive rapid HIV or syphilis test (or those who report prior syphilis infection) will also have blood drawn for confirmatory testing (10 mL or 2 teaspoons total; 8 mL for HIV testing and 2 mL for syphilis testing). Participants with active STI infections or HIV will be referred to affiliated clinics for evaluation and treatment. Participants who test positive at baseline for HIV infection will be withdrawn, however those who test positive for HIV at subsequent waves or who test positive for any STI infection at any visit will remain on study (see Case Report Forms, Appendix g). During the COVID-19 pandemic, no STI samples will be collected at any time point. HIV testing will be completed at the baseline visit only, for screening purposes, and will include the HIV In-home Oraquick test for visits initiated remotely. The HIV In-home test will be delivered to potential participants by courier prior to the baseline visit.

Completion of study assessments at each visit is expected to take 60 minutes.

*Semi-structured Interviews.* We will also examine the implementation experiences of TLC intervention participants and staff through semi-structured interviews with 20 TLC participants and 10 TLC and Chicago House staff members involved in delivery of services through the TLC intervention. The qualitative interviews will be conducted by study consultants beginning in year 2 of the study (after enrollment has begun), either in-person (when COVID-19 stay-at-home orders are lifted) or by telephone (due to COVID-19 stay-at-home requirements), and audio-recorded, transcribed, with data analyzed to describe: 1) the TLC intervention implementation process; 2) the process through which the TLC intervention impacts HIV risk behavior; and 3) the role of the intervention in addressing social determinants of health (housing, employment, legal issues, health care access). TLC participants and staff will be asked a similar set of questions to identify salient

themes pertaining to each of the three areas identified above (see Data Collection Instruments, Appendix e.).

Interviews are expected to take 60 minutes.

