### **c. Study Design**

This study will take place in Chicago, Illinois at three sites with many years of supporting HIV prevention research: Chicago House and Social Service Agency (Chicago House), Ann & Robert H. Lurie Children’s Hospital of Chicago (Lurie Children’s) and University of Chicago (U of C). Study visits will take place at Chicago House and Lurie Children’s or, due to the COVID-19 pandemic, may occur virtually via teleconference or telephone; intervention delivery will occur at Chicago House or virtually via teleconference or telephone. Primary data analysis of de-identified data will take place at U of C and Lurie Children’s.

The specific aims of the study are as follows:

1. To determine the pre-post efficacy of the TLC intervention in a single arm trial on the primary outcome: number of condomless anal sex acts without protection by PrEP in the last month among 150 sexually active, HIV-uninfected TW (ages 17 and older), with assessments at baseline, 4 and 8 months.
  - a. To assess the dose response relationship by intervention exposure (i.e., the proportion of intervention components received/expressed need) as well as exposure to specific components (i.e., employment, housing, legal, and health) on reductions in the primary outcome.
  - b. To assess mediation of intervention effects on protective processes (gender affirmation, collective self-esteem, social support) theorized to increase with intervention exposure;
2. To examine the implementation experiences of TLC intervention participants and staff through semi-structured interviews with 20 TLC participants and 10 TLC and Chicago House staff members involved in delivery of services through the TLC intervention.
3. Exploratory Aims:

- a. To describe the trajectory of PrEP indication, uptake, retention and adherence in the community-based sample over an 8-month follow-up period and evaluate the impact of the TLC intervention on the PrEP continuum of care.
- b. To explore whether reductions in HIV risk are associated with epidemiologically-linked moderators including age and race/ethnicity.

Primary Hypotheses: We hypothesize that participants in the TLC intervention will demonstrate a reduction in number of condomless anal sex acts not protected by PrEP pre-post intervention.

Primary Outcome: The primary outcome of interest is the number of condomless anal sex acts without protection by pre-exposure prophylaxis (PrEP) reported in the previous month.

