#### **i. Inclusion/Exclusion Criteria:**

*TLC Participants:* For participation in the TLC intervention, interested individuals will be screened for eligibility, based on the following criteria: (1) aged 17 and older; (2) self-identify as transgender, transsexual, woman, and/or female who was assigned male sex at birth; (3) self-reported history of sex with men in the past 4 months (4) HIV-negative via self-report, verified by HIV testing at baseline; (5) able to speak/understand English; (6) willing and able to provide informed consent/assent; (7) intention to reside in the local area throughout the 8 month follow-up period; (8) no exposure to the TLC intervention in the prior 4 months (i.e., any component).

Participants will be excluded based on the following criteria: (1) they are unable to provide informed consent due to severe mental or physical illness, or substance intoxication at the time of interview; or (2) active suicidal ideation (spontaneous report; referred immediately for treatment, and may re-screen when this is resolved). NB: Participants who report taking PrEP (regardless of level of adherence) will not be excluded given evidence of low medication adherence over time and therefore potential risk of HIV infection during the study period.

*Semi-structured interviews:* All staff who interface with TLC participants or program components and all TLC participants themselves will be eligible to participate in semi-structured interviews.

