The TransWorks Employment Program offers job readiness workshops, resume assistance, computer access, job search skill development, career counseling, and mentorship. In the TransHousing program, participants are referred to a Housing Specialist to identify tailored housing services and help to obtain documentation needed for supportive housing programs. The TransLegal program includes assistance with name change and gender marker change on identifying documents, record expungement and sealing, representation in employment and housing discrimination, representation in seeking public benefits, and misdemeanor defense. If the participant’s legal concerns fall outside of the scope of the TransLegal program, they are referred to alternative legal counsel. In the TransHealth program, TLC contracts with Heartland Health Outreach (HHO) to provide Medical Services on-site at the TransSafe drop-in program. For participants with a medical complaint, an HHO nurse practitioner meets with each individual and focuses on the presenting complaint; the medical provider also conducts a general health assessment, including sexual health risk assessment and need for cross-sex hormones and HIV prevention and treatment services. The provider makes referrals for any necessary continuing care, including PrEP initiation and care or HIV treatment services.

During COVID-19 restrictions, TLC services, including TransSafe, “TransWorks,” “TransHousing,” “TransLegal,” and “TransHealth” are offered in virtual mode, via telephone, web-based telehealth and teleconference, as well as email communication.

All study staff will receive training on human subjects’ protection, interviewing and data collection, and data handling prior to beginning engaged research activities. Study staff will be trained to remain neutral and professional in their interactions with participants and to encourage honest responses to the study questionnaire.

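### Retention in PrEP care is not tied to PrEP, so an on-site TransHealth visit (part of TLC itself) can satisfy it; for linkage the wording is only ambiguous

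*Protocol*

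**What the plan says.** Protocol III.c.i Variables (secondary outcomes) fixes three PrEP continuum outcomes, taken from self-report and confirmed by medical records abstraction.

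- Linkage: "Linkage to PrEP care is defined as attending at least one PrEP-related care visit to assess medical eligibility for PrEP initiation".
- Initiation: the date medication was started, current use and the most recent date taken.
- Retention: "at least 1 primary care visit over the 8-month follow-up period".

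Protocol III.c.ii Intervention describes the health component of TLC: "In the TransHealth program, TLC contracts with Heartland Health Outreach (HHO) to provide Medical Services on-site at the TransSafe drop-in program". A nurse practitioner sees participants who have a medical complaint, deals with that complaint, and also "conducts a general health assessment, including sexual health risk assessment and need for cross-sex hormones and HIV prevention and treatment services". Then: "The provider makes referrals for any necessary continuing care, including PrEP initiation and care or HIV treatment services".

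Protocol II.c Study Design lists, as exploratory Aim 3a, to "evaluate the impact of the TLC intervention on the PrEP continuum of care". The trial has a single arm. Under III.b.i, nobody may enter who received any TLC component in the four months before. Under III.c.i, attendance at each TLC component is logged as intervention dose.

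**The concern.** Retention in PrEP care should show that someone who started PrEP is still being followed for it. The definition asks for one primary care visit in eight months and nothing more. TransHealth offers a practitioner visit with a general health assessment, on site, as part of the intervention and within the same eight months. If that visit is accepted, delivery of TLC is recorded as a result of TLC, possibly in a participant who never took PrEP.

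Aim 3a is where this matters. No control group would show how much of the retention figure consists of programme contacts. Extra qualifying visits can raise the proportion but not lower it. Eligibility also removes TLC contacts from the four months before entry, so any before-after reading would be lopsided.

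**Working it through.** The protocol gives no figure for retention or linkage, so there is none to reproduce. The check sets the definitions against the content of a TransHealth visit.

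**Retention**

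| Condition one would expect | Required by the definition? | TransHealth visit as described |
|---|---|---|
| Visit concerns PrEP | No | Complaint-driven, with a general assessment |
| Participant has started PrEP | No | Not needed |
| Visit is outside the intervention | No | It is the intervention |
| Visit is primary care | Yes | Practitioner visit with general health assessment; fits the ordinary sense, though the protocol never uses the term for it |
| Visit falls within 8 months | Yes | TLC services run throughout that period |

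Both conditions that are required can be met by a TransHealth visit. None of the three that would exclude it is stated.

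**Linkage**

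Here the definition requires that the visit be related to PrEP and that its purpose be to assess medical eligibility. TransHealth assesses need for HIV prevention services and then refers onward. On a plain reading it comes before linkage. The definition restricts neither provider nor place, and gives no rule for separating a needs assessment from an eligibility assessment. III.d lists PrEP visit information among the files sent from Chicago House, which hosts TLC, so on-site visits may reach the data. The text permits a TransHealth visit to be counted but does not say that it is.

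**Illustration of size, retention only**

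Inputs, all assumed because the protocol gives none of them:

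- p = proportion with a qualifying visit outside TLC: 5%, 20%, 40%.
- q = proportion with at least one TransHealth visit: 10%, 25%, 50%, 75%.
- Every TransHealth visit is accepted, and the two kinds of visit are independent.

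Scored proportion = 1 − (1 − p)(1 − q). For example, p = 20% and q = 50% gives 1 − 0.80 × 0.50 = 60%.

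| p | q = 10% | q = 25% | q = 50% | q = 75% |
|---|---|---|---|---|
| 5% | 14.5% | 28.8% | 52.5% | 76.2% |
| 20% | 28% | 40% | 60% | 80% |
| 40% | 46% | 55% | 70% | 85% |

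If TransHealth visits are not counted, the result stays at p.

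Two relaxations, for p = 20% and q = 50%:

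- If the visits of only half the TransHealth users are accepted, the effective q is 0.5 × 50% = 25%, and the result is 40%.
- Without independence, the result lies between the larger of 20% and 50%, which is 50%, and their sum, 70%.

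**The case against.** Several points on the other side have weight.

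- The protocol never calls TransHealth primary care, and it has TransHealth refer participants out for continuing care. An abstractor might well not count it. This stands as a reason to say that the visit can be scored, not that it is. It does not supply the missing rule.
- Records abstraction is required, and the case report forms in Appendix g, which are not shown, may separate visit types. III.d also lists PrEP visit information apart from attendance records. Neither changes a definition that asks only for a primary care visit.
- If the on-site practitioner did carry out a PrEP eligibility work-up, that would be real linkage through co-located care. Excluding it because of where it happened would undercount. This stands and shapes the fix.
- PrEP initiation is measured separately from medication dates and use, so a programme whose referrals led nowhere would be exposed there. This also stands. It limits the harm but does not make the retention figure right.

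Three stronger readings are tempting, and the documents do not support them.

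- A reader might infer that receiving TLC is automatically scored as linkage. The linkage definition requires more than TransHealth is described as doing.
- A reader might infer that the dose-response analysis is circular, because TransHealth contacts are logged as dose. Aim 1a and III.d confine that analysis to condomless anal sex, the basis of the primary outcome. No stated analysis relates retention or linkage to dose.
- A reader might apply the arithmetic above to linkage. That would need every TransHealth visit to pass as a PrEP eligibility visit, which is not what III.c.ii describes.

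**Conclusion.** The point holds for retention. As written, one on-site TransHealth visit can be scored as retention in PrEP care, including for a participant who never started PrEP, and this would inflate one measure in the exploratory evaluation under Aim 3a. The conclusion rests on reading a practitioner's general health visit as primary care, which the protocol neither states nor rules out.

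The size cannot be derived from the protocol. The illustration shows that the overlap could dominate the figure if TransHealth is widely used and its visits are accepted. It is an upper-end picture, because it counts every TransHealth visit.

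For linkage there is an ambiguity to settle, not an error. This is a matter of outcome definition that the protocol itself fixes, so it should be corrected there.

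**What to change.** In III.c.i, under secondary outcomes:

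- **Retention.** Count only an attended visit documented as PrEP care, meaning PrEP follow-up or a PrEP prescription in the abstracted record, among participants who initiated PrEP. State that general TransHealth assessments do not count.
- **Linkage.** State that a TransHealth needs assessment or referral alone does not count. State also that any visit, on site or elsewhere, counts if the chart records a PrEP medical-eligibility work-up or prescription.
- **Abstraction form.** Record the site and type of each visit, so that the rule can be applied and checked.

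The cost is a few lines of definition and two fields on a form. Reported retention, and possibly linkage, will look less favourable. Retention among initiators will also rest on fewer people. If initiation were only the 5% that II.a reports for a cohort of younger transgender women, 120 participants at 8 months would give 120 × 0.05 = 6. The count should therefore be shown beside the proportion. These are changes to measurement only; participants' care is untouched.

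### Retention in PrEP care is met by a single primary care visit that need not concern PrEP or come after linkage or initiation

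*Protocol*

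**What the plan says.** Section III.c.i of the protocol, under Secondary outcomes, introduces the continuum as a set of linked steps: "PrEP continuum outcomes, including PrEP linkage to care, PrEP initiation and retention in PrEP care will be measured using self-report with confirmation via medical records". Three steps follow.

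- **Linkage:** "Linkage to PrEP care is defined as attending at least one PrEP-related care visit to assess medical eligibility for PrEP initiation". No time window is given.
- **Initiation:** "PrEP initiation questions will measure the date of initiation of medication, current use and most recent date the medication was taken".
- **Retention:** "Retained in PrEP care will be measured over the 8-month follow-up interval as at least 1 primary care visit over the 8-month follow-up period".

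No denominator is stated for retention. The outcome serves exploratory Aim 3a in Section II.c: "To describe the trajectory of PrEP indication, uptake, retention and adherence in the community-based sample over an 8-month follow-up period". That aim also seeks to evaluate the effect of the intervention on the continuum.

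The sample mixes users and non-users of PrEP. Use is not an entry requirement, and Section III.b.i adds that "Participants who report taking PrEP (regardless of level of adherence) will not be excluded".

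**The concern.** The linkage definition requires a visit about PrEP; the retention definition does not. It also makes no reference to the two steps before it. Retention in a continuum should describe people who entered care and stayed in it. Under this wording the label can go to someone who saw a primary care provider once, for any reason. It can also go to someone whose only PrEP contact was the eligibility visit that already counted as linkage.

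At stake is whether the reported retention proportion means what its name says. A later step that can be larger than an earlier one does not describe progress along a continuum, and a change in it cannot be read as better or worse engagement with PrEP.

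**Working it through.** The protocol gives no target, power or expected value for this outcome, so there is no figure to reproduce. The check has two parts.

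**1. The three definitions side by side**

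| Step | Visits required | Must concern PrEP? | Must follow an earlier step? |
|---|---|---|---|
| Linkage | 1 | Yes | Not applicable |
| Initiation | None (medication dates and use) | Yes | Not stated |
| Retention | 1 | No | No |

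- *Literal reading, all participants in the denominator:* any one primary care visit in the 8 months is enough. Linkage and initiation are irrelevant.
- *Narrow reading, only people in PrEP care, with the visit taken to be a PrEP visit:* a participant whose linkage visit falls within follow-up meets retention with that same visit, even if she never returns or never starts medication. For people linked during follow-up, retention would then be 100% by construction.

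**2. Illustration of size under the literal reading**

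Inputs:
- Participants at 8 months: N = 150 × (1 − 0.20) = 120 (Section III.b.ii, Sampling).
- Initiation: 5%, the background figure from an interim analysis of younger transgender women (Section II.a). Initiators I = 120 × 0.05 = 6, so non-initiators = 114.
- Probability v that a non-initiator has any primary care visit in 8 months: not in the protocol; assumed 30% to 90%.
- All initiators are assumed to have a qualifying visit.

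Formula: retained = I + (N − I) × v.

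- v = 30%: 6 + 114 × 0.30 = 40.2 (33.5% of 120)
- v = 50%: 6 + 114 × 0.50 = 63.0 (52.5%)
- v = 70%: 6 + 114 × 0.70 = 85.8 (71.5%)
- v = 90%: 6 + 114 × 0.90 = 108.6 (90.5%)

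Share of the retained who never started PrEP = (N − I) × v / retained: 34.2 / 40.2 = 85.1% at the low end and 102.6 / 108.6 = 94.5% at the high end.

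Sensitivity to the initiation rate (15% and 30% are assumptions):

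| Initiation | Initiators | Retained, v = 30% to 90% | Never started, share of retained |
|---|---|---|---|
| 5% | 6 | 40.2 to 108.6 | 85.1% to 94.5% |
| 15% | 18 | 48.6 to 109.8 | 63.0% to 83.6% |
| 30% | 36 | 61.2 to 111.6 | 41.2% to 67.7% |

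The result does not depend on every initiator having a visit. If none did, retained would equal (N − I) × v. That exceeds the number of initiators once v is above 6 / 114 = 5.3% at 5% initiation, or above 36 / 84 = 42.9% at 30% initiation.

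**The case against.** The best defence is that the retention item is the third step of a list about PrEP and carries PrEP care in its name. Section III.d refers to case report forms for PrEP care and to the transfer of PrEP medical visit information. A reading limited to people in PrEP care is therefore plausible, and an analysis plan that is not shown could set that denominator. This stands as far as it goes, and it is why the literal result is put here as what the wording allows, not as what will be reported. It does not rescue the definition, because under the narrow reading the linkage visit can still satisfy retention.

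A reader might infer four stronger things that the protocol does not support.

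- *Aim 3a cannot separate uptake from persistence.* It can. Initiation date, current use and last dose date are collected, self-reported engagement is scheduled at all three visits (Table 2), and one-month adherence is recorded by timeline follow-back. Hair or dried blood spot checks add to this outside the COVID-19 period. Only the visit-based measure fails.
- *Existing PrEP users inflate the linkage and initiation counts.* Section III.b.i says only that they may enrol. Nothing says that they are counted as newly linked or newly started, and baseline data identify them.
- *Intervention clinic visits are counted as the outcome.* TransHealth does arrange "to provide Medical Services on-site at the TransSafe drop-in program", where "an HHO nurse practitioner meets with each individual and focuses on the presenting complaint". The protocol never calls these primary care visits for this outcome.
- *Retention is simply an easier criterion than linkage.* Both need one visit. Retention is looser only in what the visit must be about. A PrEP visit outside primary care could count for linkage and not for retention, so neither criterion contains the other.

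**Conclusion.** The point holds in limited form. The protocol states a retention rule that does not measure retention: the visit need not concern PrEP and need not follow linkage or initiation. This is a fault in a definition that is given, not a detail left for later.

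Under the literal reading with everyone in the denominator, about 40 to 109 of 120 participants could be called retained against 6 initiators. That range rests on the assumed 30% to 90% visit rate and on carrying over a 5% initiation figure from another sample. At an assumed 30% initiation the excess shrinks but remains: about 61 to 112 retained against 36 initiators. Under the narrow reading these counts do not apply, and the fault is the overlap with linkage.

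The effect is confined to one component of a secondary outcome and to exploratory Aim 3a. The primary outcome and the sample size are not affected, and persistence on medication can still be described from the other PrEP data. It should be corrected before analysis.

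**What to change.** Change the definition in Section III.c.i as follows.

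- **Denominator:** participants who initiated PrEP during the study or were taking it at baseline.
- **Event:** at least one PrEP-related care visit dated after initiation (after baseline for those already on PrEP), and distinct from the linkage visit.
- **Late starters:** report separately those who start too close to month 8 to have had a follow-up visit, so that they are not counted as failures.

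Derive the measure from data already planned: self-report, record abstraction after the 8-month visit, and the PrEP visit information transferred for analysis. Confirm first that visit dates are captured, because the protocol text names the medication initiation date but not the dates of visits. Abstraction also depends on a current release of information, so state what happens when there is none.

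The cost is a redefinition and a revised derivation, with a possible added date field. The denominator will be smaller, the estimate less precise and the retention percentage lower.
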